8.3 STATISTICAL ANALYSES

8.3.1 GENERAL APPROACH

Analyses will be performed on an intent-to-treat basis (ie, participants will be analyzed by the arms to which they were randomized). All statistical tests will be two-sided. All analyses will be performed using SAS, and *P*<.05 will be deemed statistically significant.

Although a large amount of missing data is not expected for any of our study variables, a sensitivity analysis may be performed using alternative methods for handling missing data (such as multiple imputation) to assess the most appropriate approach based on the amount of missing data and effect sizes observed.

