8.2 SAMPLE SIZE DETERMINATION

Results from our previous UAB pilot study indicated an increase in minutes of moderate-to-vigorous physical activity among the DIAL intervention group compared with the control group. The SD of this measure was 90 minutes. Assuming a mean difference of 35 (SD 90) minutes in moderate-to-vigorous physical activity between the two groups from baseline to 6 months, a two-tailed two-group t test, and a significance level of 5%, we will have 80% power to detect this difference (with an effect size of 0.388) with 105 participants per arm (210 for the study). Assuming a mean change of 35 (SD 90) minutes in moderate-to-vigorous physical activity from baseline to 6 months for the intervention group, a two-tailed paired t test, and a significance level of 5%, we will have 80% power to detect this within-group change (with an effect size of 0.276) with 105 participants. Allowing for 15% attrition, we will recruit 240 participants (120 per arm).

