8.3.2 ANALYSIS OF THE PRIMARY EFFICACY ENDPOINT(S)

The primary method of analysis for physical activity, anthropometrics, and psychosocial measures, all of which will be measured at baseline, 6 months, 12 months, and 18 months, will be mixed model repeated measures analyses. Other general linear mixed model techniques may also be used. These analyses will allow us to examine changes from baseline to follow-up (within-group changes) and differences between the study groups simultaneously, while also accounting for the group-by-time interaction as well as any covariates and interactions that are of scientific interest. An appropriate covariance matrix (eg, autoregressive or unstructured) will be selected based on the final data. The Tukey-Kramer multiple comparisons test will be used to determine specific pairwise differences for statistically significant main effects. Some of these models will include the stratification variable of county and confounding variables (as covariates) such as the baseline BMI category, age, gender, and education level. Some of the models that include physical activity as the dependent variable will be adjusted for wear time. Study variables that will be analyzed using these techniques include the change in minutes of moderate-to-vigorous physical activity. Pearson correlation analysis will be performed to assess the relationship between self-reported and measured physical activity.

Distributions of the aforementioned continuous variables will be examined for normality using box plots, normal probability plots, and the Kolmogorov-Smirnov test. Variables that are determined to deviate from a normal distribution will be log-transformed before statistical testing. Nonparametric tests (eg, the Wilcoxon rank-sum test and the Wilcoxon signed-rank test) may also be used to analyze nonnormally distributed data.

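### The only alternative missing-data method named, multiple imputation, as usually run shares the primary mixed model's missing-at-random assumption, so agreement between the two would not test whether DIAL dropouts lost the benefit

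*Combined protocol and SAP*

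**What the plan says.** Section 8.3.1 sets an intent-to-treat analysis in which "participants will be analyzed by the arms to which they were randomized". Section 8.3.2 states that the primary method for physical activity "will be mixed model repeated measures analyses".

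The only provision for missing data is in section 8.3.1. It opens with "Although a large amount of missing data is not expected for any of our study variables" and goes on to say that "a sensitivity analysis may be performed using alternative methods for handling missing data (such as multiple imputation"). The stated purpose is "to assess the most appropriate approach based on the amount of missing data and effect sizes observed". The imputation model, its assumption and any auxiliary variables are not given.

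No control-based, delta-adjusted, pattern-mixture or tipping-point analysis appears anywhere. Section 8.3.5 compares completers with dropouts on baseline characteristics only.

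Section 8.2 gives the planning figures: "Assuming a mean difference of 35 (SD 90) minutes in moderate-to-vigorous physical activity between the two groups from baseline to 6 months", and "Allowing for 15% attrition, we will recruit 240 participants (120 per arm").

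**The concern.** The trial is to estimate the effect of DIAL in everyone randomised. Section 7.1 has accelerometry at baseline and at 6, 12 and 18 months, and section 3.1 has the 7-Day PAR at the same visits. Someone who leaves for good before month 6 therefore has one MVPA value, at baseline. Under missing at random, the mixed model fills the gap from participants in the same arm who stayed, given baseline and any covariates. Ordinary multiple imputation does the same by drawing values. If DIAL participants who leave have also stopped exercising, both methods credit them with a benefit they do not have, and both do so by about the same amount.

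The protocol gives some reason to consider this. Section 6.2 lets the investigator withdraw a subject for significant non-compliance with the intervention, so a missing outcome can follow directly from not doing DIAL. The baseline comparison in section 8.3.5 cannot show what happened to MVPA after dropout.

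The 6-month result also carries forward. In section 8.3.3 the cost-effectiveness analysis is run only if DIAL significantly increases MVPA. It covers 6 months and uses MVPA change as one of its effectiveness measures.

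**Working it through.** **Inputs.** From section 8.2: difference 35 minutes, SD 90, two-sided 5%, 80% power, 105 per arm, 15% attrition, 120 recruited per arm. The documents do not give attrition by arm, attrition by month 6, or the outcome of dropouts. These are assumptions below.

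**The plan's own figure.** The effect size is 35/90 = 0.389 (plan: 0.388). The normal approximation gives n = 2 × (1.960 + 0.842)² × (90/35)² = 103.8, so 104 per arm. The t test gives 104.8, so 105 per arm, with power 80.1%. The plan's 105 reproduces.

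**Formula.** Measure MVPA change relative to wait-list stayers. DIAL stayers have effect 35. Let q be the share of the DIAL arm lost by month 6 and e the mean effect in those lost. Take wait-list dropouts to be like wait-list stayers for now.

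- Missing-at-random estimate (mixed model or ordinary multiple imputation): 35
- Effect in all randomised: (1 − q) × 35 + q × e
- Overstatement: q × (35 − e)

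**Results.** With q = 0.15 and e = 0, the effect in all randomised is 0.85 × 35 = 29.75. The overstatement is 0.15 × 35 = 5.25 minutes, and 5.25/35 = 15%.

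| DIAL loss by month 6 | Dropout effect e | Effect in all randomised | Overstatement | % of 35 |
|---|---|---|---|---|
| 10% | 0 | 31.5 | 3.5 | 10% |
| 12.5% (210 of 240 evaluable) | 0 | 30.6 | 4.4 | 12.5% |
| 15% | 0 | 29.75 | 5.25 | 15% |
| 20% | 0 | 28.0 | 7.0 | 20% |
| 15% | 17.5 (half kept) | 32.4 | 2.6 | 7.5% |
| 15% | 35 (all kept) | 35 | 0 | 0% |
| 15% | −17.5 (below control) | 27.1 | 7.9 | 22.5% |

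**Wait-list dropouts.** Let a share r of the wait list be lost, with mean w relative to wait-list stayers. The overstatement becomes q × (35 − e) + r × w. With q = r = 0.15, e = 0 and w = −35, it is 5.25 − 5.25 = 0.

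**Simulated check.** One run with 200,000 per arm, 15% lost in each arm and e = 0, using arm means only, gave: all randomised 29.7, observed-data estimate 34.8, ordinary multiple imputation 34.7, control-based imputation 29.5. The scenario was imposed. The run shows only that, in this scenario, ordinary imputation follows the observed-data estimate and control-based imputation recovers the value in all randomised.

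**The case against.** The strongest objection is that the plan does not commit to missing-at-random imputation. It speaks of alternative methods, gives multiple imputation as an example and states no model. Control-based and delta-adjusted analyses are themselves multiple imputation, so the wording permits them. An imputation could also draw on the 3-month surveys and the IVR activity reports, which the mixed model as described does not use. This stands in part. A reader might infer that multiple imputation must share the mixed model's assumption, and the documents do not support that. But the plan specifies none of these variants. Auxiliary data could weaken the assumption but would not show what happens if it fails.

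Three other readings go too far.

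- **15% as a ceiling.** Section 8.2 gives attrition overall, neither split by arm nor tied to month 6. The gap could be smaller or larger.
- **A certain bias in favour of DIAL.** The documents do not say that dropouts stop exercising or lose all benefit, and worse outcomes among wait-list dropouts could offset the gap.
- **Agreement will be reported as robustness.** Section 8.3.1 states a different purpose, namely choosing the approach.

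It is also fair to say that not every missing month-6 value belongs to a permanent dropout. The PAR is taken by phone, so a missed visit need not mean a missing PAR. Section 6.3 requires two missed visits and failed contact before someone counts as lost. A participant who returns at month 12 contributes to the mixed model. The remedy should therefore not treat every missing month-6 value as a control value.

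**Conclusion.** The concern holds in a limited form. No planned analysis lets DIAL dropouts have lost the benefit, and the one alternative named would, as usually run, repeat the primary model's assumption. For participants lost for good before month 6, agreement between the two would say nothing about that assumption.

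On the plan's figures the overstatement is 5.25 minutes (15% of 35) if three things hold: 15% of the DIAL arm is lost by month 6, those lost are at the control mean, and stayers have the full 35-minute effect. It also takes wait-list dropouts to resemble wait-list stayers. This is one scenario within a range that includes zero.

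The primary model need not change. The point is an inexpensive improvement to what the trial can conclude, not a flaw that invalidates the analysis. Section 8.3.1 does not expect much missing data, but that does not settle the matter when section 8.2 itself allows for 15%.

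**What to change.** Keep the mixed model as primary. In section 8.3.1, replace the optional sentence with a pre-specified sensitivity analysis of the 6-month between-arm MVPA contrast that departs from missing at random, using one or both of:

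- **Control-based multiple imputation.** For DIAL participants who have left the study before month 6, impute month-6 MVPA from the wait-list arm given baseline MVPA, county and BMI group. Participants still in the study who merely miss the month-6 measurement are not imputed this way.
- **Delta-adjusted (tipping-point) imputation.** Shift the imputed values in pre-stated steps on the scale used for analysis, keeping MVPA at or above zero. The scale matters because section 8.3.2 provides for log transformation.

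Report the result beside the primary estimate. Do not cite agreement with ordinary multiple imputation as evidence of robustness to dropout. No pass/fail rule is needed: t-test power for 29.75 minutes is only 66.4% at 105 per arm, so requiring significance there would be a demanding gate.

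Limit the control-based version to month 6. Section 3.1 offers wait-list participants DIAL after that assessment, so their later values no longer represent an untreated reference.

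The cost is one paragraph of text and a little extra SAS programming, with no new data or participants. The downside is that the sensitivity estimate may be less favourable than the primary one, at about 30 rather than 35 minutes in the illustrated scenario.

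### The plan names the observed effect sizes as a criterion for judging the missing-data approach, and leaves the sensitivity analysis optional

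*Combined protocol and SAP*

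**What the plan says.** Three sections bear on this.

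- **Section 8.3.1 (General Approach)** sets the expectation: "Although a large amount of missing data is not expected for any of our study variables". It then says that "a sensitivity analysis may be performed using alternative methods for handling missing data (such as multiple imputation"), and gives the purpose, which is to judge what approach suits best "based on the amount of missing data and effect sizes observed". The same section commits to intention to treat: "Analyses will be performed on an intent-to-treat basis (ie, participants will be analyzed by the arms to which they were randomized").
- **Section 8.3.2 (Analysis of the Primary Efficacy Endpoint(s))** says that the primary method for physical activity "will be mixed model repeated measures analyses". It adds: "Other general linear mixed model techniques may also be used". It leaves the covariance structure to be selected from the final data. It does not say how the model treats missing values or under what assumption.
- **Section 8.2 (Sample Size Determination)** sizes recruitment "Allowing for 15% attrition".

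No section gives a missingness assumption, a threshold for a large amount of missing data, a duty to report every method that is run, or a statement that the approach is chosen blind to arm.

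**The concern.** A sensitivity analysis asks whether the conclusion survives a different assumption about the missing values. Section 8.3.1 gives it another purpose, which is to settle which approach is most appropriate, and one of its two criteria is the size of the effect found. If several methods are run and the preferred one is identified partly by its estimate, the reported p-value no longer has its nominal meaning and the other analyses stop serving as a check.

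The optional status adds to this. The plan budgets for 15% attrition, which is 0.15 × 120 = 18 participants per arm, yet it commits to no sensitivity analysis. The protocol also gives reasons why missingness could differ by arm. Section 6.2 allows withdrawal for marked non-compliance with the intervention, and under section 3.1 only the DIAL arm receives the intervention before 6 months. For the accelerometer measure, the valid-wear rule in section 8.1 is a further source of missing values.

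**Working it through.** **1. The plan's own figure.** Section 8.2 gives a difference of 35 minutes, SD 90, two-sided 5% and 80% power. The effect size is 35/90 = 0.389. A two-sample t test needs 104.8, so 105 per arm, and power at 105 is 80.1%. The stated 105 per arm is reproduced. The point does not rest on it.

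**2. What the text fixes and what it leaves open.**

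| Question | Answer in the plan |
|---|---|
| Is a primary model named? | Yes, mixed model repeated measures (8.3.2) |
| Is it the only model allowed? | No, other mixed-model techniques are permitted (8.3.2) |
| Is its missing-data assumption stated? | No |
| Is a sensitivity analysis required? | No, it is optional (8.3.1) |
| What decides which approach is most appropriate? | Amount of missing data and observed effect sizes (8.3.1) |
| Is a sensitivity result barred from becoming the main result? | No such statement |

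**3. Size when the methods agree closely.** A simulation under no true effect used 120 per arm, SD of change 90 and 6,000 runs per scenario. These inputs are assumptions, not taken from the documents: data missing completely at random, baseline-change correlation −0.3, a mean change of 20 minutes in both arms, and the choice of methods (complete-case t test, multiple imputation, baseline carried forward). The mixed model itself was not simulated. The result counted is whether any method reaches P<.05.

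| Missing | Each method alone | Better of complete case and imputation | Best of all three |
|---|---|---|---|
| 15% (plan) | 4.7–4.8% | 5.3% | 5.5% |
| 30% (assumed) | 4.7–4.9% | 5.7% | 6.2% |

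Monte Carlo error is about 0.3 points: √(0.055 × 0.945 / 6000) = 0.0029.

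**4. Size when the methods agree less.** For k analyses whose null test statistics are standard normal with common correlation r, and c = 1.96, the chance that at least one is significant is

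1 − ∫ φ(w) [Φ((c − √r·w)/√(1−r)) − Φ((−c − √r·w)/√(1−r))]^k dw.

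| r | k = 2 | k = 3 |
|---|---|---|
| 0.996 | 5.4% | 5.6% |
| 0.98 | 5.9% | 6.5% |
| 0.95 | 6.5% | 7.3% |
| 0.90 | 7.0% | 8.4% |
| 0.80 | 7.8% | 9.8% |

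A separate simulation at 15% missing completely at random gave correlations of 0.996 (complete-case ANCOVA against imputation) and 0.98 to 0.99 (against baseline carried forward). That places the benign case in the top two rows, about 5.4% to 6.5%. The value 0.9 is assumed and is not derived from any missingness mechanism in the documents.

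All these figures count significance in either direction. The share favouring DIAL is half: at r = 0.9, 7.0/2 = 3.5% and 8.4/2 = 4.2%, against a nominal 2.5%.

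**The case against.** The best defence is that the sentence concerns an optional sensitivity analysis, while section 8.3.2 separately names the primary method and section 8.3.1 commits to analysis by randomised arm. Comparing effect estimates across methods is what a sensitivity analysis does, and the phrase could mean only that. On this reading nothing is chosen by its result, and the wording is merely loose.

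Much of this stands. A reader might infer that the plan lets the result choose the primary method outright. The documents do not say so: a primary model is named, the effect size is one of two criteria, and no section states that a sensitivity analysis may replace it. What does not stand is the claim that the matter is therefore closed. The stated purpose is to settle on an approach, not to test robustness, and the primary model is itself only partly fixed.

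The objection on size also stands for the planned case. At 15% missing completely at random the methods nearly coincide, so an inflation of 2 to 3 points should not be presented as the expected one. That needs the lower correlation, which is assumed.

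A reader might also point out that if the 15% of DIAL participants who drop out keep no gain, a 35-minute effect becomes 0.85 × 35 = 29.75 minutes. That shows that the assumption about dropouts can move the estimate. It does not measure the harm of choosing a method by its result, and it assumes no arm difference among dropouts, which the documents do not state.

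**Conclusion.** The point holds as a defect of wording with a real but probably modest consequence. An outcome-dependent criterion is written into section 8.3.1, and no other section neutralises it.

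The inflation of type I error is about 0.3 to 0.5 points above nominal (5.3% to 5.5%) at the planned 15% attrition, given missing completely at random, a baseline-change correlation of −0.3 and the methods simulated. It could reach about 7.0% (two analyses) or 8.4% (three) if the test statistics correlate only 0.9. Missingness that differs by arm would push the methods apart. The documents give no dropout rate by arm, so how far cannot be worked out from them. All these figures suppose that a significant result from any method is always the one kept, so for a given degree of agreement they are the worst case. The case for changing the text does not depend on which figure applies.

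**What to change.** Three edits to the SAP text:

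1. In section 8.3.1, strike the last four words of "based on the amount of missing data and effect sizes observed", and describe the sensitivity analysis as a check on robustness, not as a way to select an approach.
2. In section 8.3.2, state that the mixed model, fitted to all randomised participants under a missing-at-random assumption, stays primary whatever the sensitivity analyses show.
3. In section 8.3.1, make the sensitivity analysis mandatory by changing the permissive verb in "a sensitivity analysis may be performed using alternative methods for handling missing data (such as multiple imputation") to a commitment. Name one analysis in advance and report it whatever it shows. Multiple imputation with a missing-not-at-random scenario is one example. The documents do not dictate a particular version, so the trial team should choose it before arm-level outcome data are seen.

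The cost is SAP wording and one extra analysis. No new data and no change to the sample size are needed for this point.

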8.3.2 ANALYSIS OF THE PRIMARY EFFICACY ENDPOINT(S)

The primary method of analysis for physical activity, anthropometrics, and psychosocial measures, all of which will be measured at baseline, 6 months, 12 months, and 18 months, will be mixed model repeated measures analyses. Other general linear mixed model techniques may also be used. These analyses will allow us to examine changes from baseline to follow-up (within-group changes) and differences between the study groups simultaneously, while also accounting for the group-by-time interaction as well as any covariates and interactions that are of scientific interest. An appropriate covariance matrix (eg, autoregressive or unstructured) will be selected based on the final data. The Tukey-Kramer multiple comparisons test will be used to determine specific pairwise differences for statistically significant main effects. Some of these models will include the stratification variable of county and confounding variables (as covariates) such as the baseline BMI category, age, gender, and education level. Some of the models that include physical activity as the dependent variable will be adjusted for wear time. Study variables that will be analyzed using these techniques include the change in minutes of moderate-to-vigorous physical activity. Pearson correlation analysis will be performed to assess the relationship between self-reported and measured physical activity.

Distributions of the aforementioned continuous variables will be examined for normality using box plots, normal probability plots, and the Kolmogorov-Smirnov test. Variables that are determined to deviate from a normal distribution will be log-transformed before statistical testing. Nonparametric tests (eg, the Wilcoxon rank-sum test and the Wilcoxon signed-rank test) may also be used to analyze nonnormally distributed data.

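### Section 8.3.2 does not pre-specify adjustment for baseline MVPA, so the primary arm contrasts may be less precise than the same data allow

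*Combined protocol and SAP*

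**What the plan says.** Section 3.1 makes change in physical activity from baseline to 6 months and to 12 months the primary endpoints. Section 8.3.2 analyses physical activity by a mixed model for repeated measures, with baseline, 6, 12 and 18 months as the measured occasions and a group-by-time interaction. It adds: "Study variables that will be analyzed using these techniques include the change in minutes of moderate-to-vigorous physical activity". Some models will also include county and covariates "such as the baseline BMI category, age, gender, and education level", and some will be adjusted for wear time. Any further covariate of scientific interest is allowed, as are other mixed-model techniques.

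Baseline MVPA is not named as a covariate anywhere, and no constraint of equal baseline means is stated. ANCOVA appears only in the abbreviation list (section 9.2).

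The sample size in section 8.2 rests on an unadjusted two-group t test: "Assuming a mean difference of 35 (SD 90) minutes in moderate-to-vigorous physical activity between the two groups from baseline to 6 months". On the source of the SD it says only: "The SD of this measure was 90 minutes".

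**The concern.** The two natural readings of section 8.3.2 lead to the same estimate. If change is the outcome, the arm effect is the difference in mean change. If baseline is a repeated response with a separate mean in each arm, the group-by-time contrast with complete data is again the difference in mean change. Either way the coefficient on baseline is fixed at 1 instead of being estimated, and the equality of baseline means that randomisation provides is not used.

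The cost is possible loss of precision. Section 5.2 stratifies by BMI group because BMI is related to activity. Baseline activity is a more direct predictor of later activity, and section 3.1 has it measured on everyone before randomisation.

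There is also a pre-specification cost. Because the covariate list is open and applies only to some models, the decision whether to adjust for the outcome's own baseline value can be taken after the results are known.

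**Working it through.** **Inputs.** From section 8.2: difference 35 min, SD 90 min, two-sided 5%, 105 per arm, 15% attrition, 240 recruited. From section 4.1: entry requires MVPA below 60 min/week. Not in the documents, and so varied below: the baseline SD (s_B), the baseline-to-follow-up correlation (rho), and the slope b of follow-up MVPA on baseline MVPA. SD 90 is read as the SD of the baseline-to-6-month change, which is an assumption because section 8.2 does not say.

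**1. The plan's figure.** With d = 35/90 = 0.389, the two-sample t test (noncentral t) needs 104.8, so 105 per arm, and has 80.1% power at 105. The stated sample size reproduces. With 15% loss from 120 per arm, 120 × 0.85 = 102 remain and power is 78.9%. That is the unadjusted reference below.

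**2. Effect of conditioning on baseline.** Residual variance after adjustment = Var(change) − (b − 1)² × s_B². In large samples this never exceeds Var(change), and it equals it only when b = 1.

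**3. Baseline MVPA inside the entry limit.** A variable confined to 0-60 has SD at most 30 (half at 0, half at 60). If uniform, its SD is 60/√12 = 17.3. With Var(change) = 90² = 8100 and 102 per arm:

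| s_B | b | Adjusted variance | Ratio to 8100 | Power |
|---|---|---|---|---|
| 17.3 | 0 | 8100 − 300 = 7800 | 0.963 | 80.4% |
| 17.3 | 0.5 | 8100 − 75 = 8025 | 0.991 | 79.3% |
| 30 | 0 | 8100 − 900 = 7200 | 0.889 | 83.4% |
| 30 | 0.5 | 8100 − 225 = 7875 | 0.972 | 80.0% |
| any | 1 | 8100 | 1.000 | 78.9% |

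The variance reduction is 0-4% for a uniform baseline and at most 11% in the extreme case.

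**4. Baseline and follow-up SDs equal.** The variance ratio becomes (1 + rho)/2. With the SD of change held at 90, s_B = 90/√(2(1 − rho)).

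| rho | Variance ratio | Implied s_B | Power at 102 per arm |
|---|---|---|---|
| 0.3 | 0.65 | 76 | 92.9% |
| 0.5 | 0.75 | 90 | 89.1% |
| 0.6 | 0.80 | 101 | 87.1% |

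The variance reduction is 20-35%, but it needs a baseline SD of 76-101 min, against a ceiling of 30 under the entry limit.

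**5. Between the two.** With r = baseline SD / follow-up SD, the variance ratio is (1 − rho²)/(1 + r² − 2 rho r) and b = rho/r. At r = 0.5 and rho = 0.3, 0.5, 0.6 the slopes are 0.6, 1.0, 1.2 and power is 80.6%, 78.9%, 79.5%. Even here the implied s_B is 46-56 min, above 30.

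**6. Chance baseline imbalance.** A difference in change has expectation (true effect) + (b − 1) × (baseline difference), given the baselines. The 95% range of the second term is ±1.96 × s_B × √(2/n) × |b − 1|. At the planned 105 per arm and b = 0 this is ±4.7 min for s_B = 17.3 and ±8.1 min for s_B = 30, against a 35-min target. At b = 1 it is zero.

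**The case against.** The best case for the plan is that its contrast is already valid and that little is lost. Both parts largely stand. A change-score comparison in a randomised trial is unbiased, and the stated sample size reproduces. A restricted baseline with a wider follow-up distribution can push the slope towards 1 or above, and near 1 a change score loses little.

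Three stronger readings are tempting, and the documents do not support them.

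- A reader might infer that the analysis rules out baseline adjustment. Section 8.3.2 leaves the covariate set open, so the accurate statement is that adjustment is not pre-specified.
- A reader might infer that any chance baseline difference passes in full into the estimate. Only (b − 1) times it does. That part is chance error already reflected in the standard error, not bias.
- A reader might infer that adjustment would lift power to about 90%. That needs the spread in step 4, which an entry limit of 60 min/week makes unlikely for the same measure.

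The limit may not bind, however. Section 3.1 applies eligibility at a brief screening interview. The baseline 7-Day Physical Activity Recall (PAR) is a later telephone interview, and no rule re-applies the cutoff to it. The primary aim in section 1.1 also covers accelerometer MVPA, which the documents do not say was used for screening. A larger gain is therefore possible, but nothing in the documents shows it.

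Power just under 80% at 102 per arm comes from the attrition allowance in section 8.2. It serves here only as the reference.

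**Conclusion.** The point holds as a weakness of efficiency and pre-specification. It does not invalidate the analysis or the stated sample size. Under both natural readings of section 8.3.2 the arm contrast is a difference in raw mean change, and baseline MVPA is not a named covariate.

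The gain cannot be fixed from the documents. The range best supported by the entry criterion is a 0-11% fall in variance, with power moving from 78.9% to at most 83.4% (slope 0 to 1, baseline SD at most 30). A fall of 20-35%, with power of 87-93%, would need baseline and follow-up SDs to be about equal. That could occur only if baseline recall or accelerometer values spread well beyond the screening report.

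All figures assume that SD 90 is the SD of change, 102 per arm, untransformed minutes and a t test. They do not carry over directly if the log-transform or rank-test fallback in section 8.3.2 is used.

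**What to change.** In section 8.3.2, name one primary MVPA model, in either of two forms:

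- MVPA at 6, 12 and 18 months as the response, with arm, visit, arm-by-visit, baseline MVPA and baseline MVPA-by-visit as fixed effects; or
- a constrained longitudinal model that keeps baseline in the response vector but fits one common baseline mean for both arms.

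Take both the 6-month and the 12-month arm contrasts from that model, since section 3.1 makes both primary. If MVPA is log-transformed, transform baseline and follow-up alike. Use the same form for the step test, anthropometric and psychosocial outcomes, which the MVPA entry limit does not truncate. State in section 8.2 whether SD 90 refers to change or to a single visit.

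The cost is SAP wording, a few lines of SAS and about one degree of freedom per visit slope. No new data are needed, because baseline MVPA is collected before randomisation.
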